#### **6.3.2.3. Definition of Toxicity Grades**

Toxicity grades will only be derived for laboratory tests for which toxicity grades are available.

Toxicity grades will be determined as implemented in the attached table ([Appendix I](#)).

For elevations (H1 to H4), values under the threshold of H1 are reported as 'Grade 0'. For elevations (L1 to L4), values above the threshold of L1 are reported as 'Grade 0'.

#### **6.3.2.4. Definition of Non-Graded Abnormalities**

For all laboratory tests provided by the laboratory, the position of the actual analysis values versus their normal ranges will be determined directly by using the position indicator provided in the database as provided by the lab, expressing the classes for these analysis values as low (L), normal (N) or high (H). L, N and H are further referred to as non-graded abnormalities.

### 6.3.2.5. Urinalysis Tests with Categorical Results

Results of urinalysis with qualitative results will be tabulated by time point. No toxicity grading or non-graded abnormalities will be derived for these tests.

### 6.3.2.6. Treatment-Emergent Principle

#### Toxicity Grades

A post-baseline toxicity grade 1, 2, 3 or 4 is defined as treatment-emergent when higher than the toxicity grade of the baseline result or when there is a change in direction (from H to L or from L to H). If the baseline result is missing, a post-baseline toxicity grade 1, 2, 3 or 4 will be considered as treatment-emergent.

#### Non-graded Abnormalities

A post-baseline non-graded abnormality class L or H is defined as treatment-emergent when it differs from the abnormality class of the baseline result. If the baseline result is missing, a post-baseline abnormality L or H will be considered as treatment-emergent.

### 6.3.2.7. Worst-Case Principle

#### Toxicity Grading

The worst-case post-baseline toxicity grade 0, 1, 2, 3 or 4 will be determined per subject, per laboratory test (and direction, increases and decreases) and for each analysis period, using all non-missing post-baseline records (including unscheduled and FU visits).

The worst-case toxicity grade is the highest toxicity grade corresponding to the highest laboratory test value (by direction, increases and decreases). In case of several equal highest post-baseline actual values, the earliest occurrence will be taken for the analyses and will be flagged in the listings.

- Grade 0: all post-baseline toxicity grades are classified as 0
- Grade 1: all post-baseline toxicity grades are classified as  $\leq 1$
- Grade 2: all post-baseline toxicity grades are classified as  $\leq 2$
- Grade 3: all post-baseline toxicity grades are classified as  $\leq 3$
- Grade 4: all post-baseline toxicity grades are classified as  $\leq 4$

If any record is missing, then the toxicity grade is considered as ‘missing’.

#### Non-graded Abnormalities

The following worst-case post-baseline abnormalities L, N or H will be determined per subject, per laboratory test and for each analysis period, using all non-missing post-baseline records (including unscheduled and FU visits):

- L = low: at least one post-baseline result is classified as L.
- N = normal: all post-baseline results are classified as N.
- H = high: at least one post-baseline result is classified as H.

If, for a subject, both L and H are reported, the subject will be counted twice in the table: once with a worst-case L and once with a worst-case H.

### 6.3.2.8. Hepatotoxicity

Hepatotoxicity will be investigated by tabulating the aspartate aminotransferase (AST) and alanine aminotransferase (ALT) values categorized as  $>3$ ,  $>5$ ,  $>10$  and  $>20$  times their upper limit of normal (per analyte and over both analytes combined), ALP categorized as  $> 1.5$  times the upper limit and total bilirubin as  $> 2$  times the upper limit of normal. Elevations of AT (AST or ALT)  $> 3$  times their upper limits accompanied by elevated total bilirubin ( $>1.5 \times \text{ULN}$ ,  $>2 \times \text{ULN}$ ) on the same day will also be tabulated.

To assess the potential of the drug to cause severe liver damage, possible Hy's Law cases will be identified. These subjects are defined as having any elevated AT (AST or ALT) of  $>3 \times \text{ULN}$ , ALP  $<2 \times \text{ULN}$ , and associated with an increase in total bilirubin  $>2 \times \text{ULN}$  on the same day.

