Calcium, phosphate, creatinine and N-acetyl- β -D-glucosaminidase (NAG). The urine protein to creatinine ratio will be derived.

– **Serology/blood:**

HBs Ag, (if positive, confirmed by HBV DNA PCR), HCV (Ab and/or PCR) and HIV 1 and 2 antibodies (at screening). Positive hepatitis and HIV results should be reported by the investigator as required by local law.

FSH test for females of (nonsurgical) nonchildbearing potential at screening to confirm menopause, if applicable.

– **Pregnancy test for females:**

Serum beta human chorionic gonadotropin at screening, baseline (Visit 1), Day 29 (Visit 4), and Day 43 (Visit 5) or ED, if applicable (all female subjects).

– **QuantiFERON-TB Gold test** to check for latent or active TB (at screening). TB results should be reported by the investigator as required by local law.

– **Stool culture/ Stool sample for microbiology/microbiome evaluation:**

For enteric pathogens, *Clostridium difficile* cytotoxin assay and microscopic examination for intestinal parasites/ova in stool sample; *Escherichia coli*, *Salmonella* species (spp), *Shigella* spp, *Campylobacter* spp and *Yersinia* spp assay in stool culture (at screening).

Note: Details of microbiome assessment are provided in Section 8.7.3.2.

– **SARS-CoV-2:**

RT-PCR from a nasal swab sample to check for SARS-CoV-2 infection at screening and RT-PCR from a nasal swab sample and serology testing at baseline, and throughout the study as needed (when SARS-CoV-2 symptoms present)

The clinical laboratory evaluations will be performed at visits specified in the Schedule of Activities in Section 8.11 (see also Section 8.1, “[Timing of Assessments](#)”). Reference ranges will be supplied by the local and central laboratory, as needed.

Clinical laboratory values outside the normal range will be flagged and clinical relevance will be assessed by the investigator. Only laboratory test abnormalities judged as clinically significant by the principal investigator should be recorded as AEs. At the discretion of the investigator, when following up AEs, additional laboratory parameters may be tested, and additional samples taken.

In case of safety issues, as per decision of the investigator, the local laboratory at site could be used to verify some parameters.

An estimate of the ClCr based on the serum creatinine level will be calculated by the central laboratory using the Cockcroft-Gault formula (see [Definition of Terms](#)).

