Appendix 9: Algorithm for Elevated Liver Function Tests

| | AST or ALT increase to | | | | |
|------------------------|---|---|---|---|-----------------------------|
| Value Range | $\geq 1.5x$ to $3x$ ULN | $\geq 3x$ to $<5x$ ULN | $\geq 5x$ to $<8x$ ULN | $\geq 3x$ ULN with signs of liver damage ¹ | $\geq 8x$ ULN |
| IP Action | Continue as planned | Reduce or interrupt IP for at least 2 weeks | Interrupt IP for at least 2 weeks Close observation ² | Discontinue IP ² | Discontinue IP ² |
| | | | | | |
| After at least 2 weeks | AST and ALT $<3x$ ULN | AST or ALT $\geq 3x$ ULN | | | |
| | Weekly LFTs for the first 2 weeks (biweekly for the following weeks, or more frequently at investigator's discretion) | Discontinue IP Report SAE and complete liver event page for any of abnormalities listed below ³ : 
 - AST/ALT increase $\geq 8x$ULN - AST/ALT increase $\geq 3x$ULN with signs of liver damage¹ | | | |

¹ Signs of liver damage:

- total bilirubin $\geq 2.0x$ ULN OR international normalized ratio >1.5 , and/or
- symptoms: appearance of fatigue, nausea, vomiting, right upper abdominal quadrant pain or tenderness, fever, rash and/or eosinophilia ($>5\%$)

² Close observation recommendations:

- Monitor 2 to 3 times per week all of the following parameters: ALT, AST, alkaline phosphatase, total bilirubin, eosinophils, INR. If local regulations allow, home visits can be performed if subjects cannot come to the clinical study center.
- Frequency of retesting can be reduced to once a week or less if abnormalities stabilize or the IP has been discontinued; however, monitoring might still be needed more frequently taking into consideration the standard of care and/or changes to this.
- Based upon investigator's discretion gastroenterology or hepatology consultations, additional serology testing, imaging and pathology assessments may be required.
- Re-query history of symptoms, prior and concurrent diseases, concomitant medication and non-prescription medicines, herbal, dietary supplements, alcohol use, recreational drug use, special diets.
- Rule out all of the following: acute viral hepatitis, autoimmune hepatitis, alcoholic hepatitis, non-alcoholic fatty hepatitis, hypoxic/ischemic hepatitis, biliary tract disease, and cholestasis.
- Re-query exposure to environmental chemical agents.

³ The following steps should be followed:

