### **6.3.2. Laboratory Safety**

#### **6.3.2.1. Available Data**

Laboratory tests scheduled are described in the CSP section 8.5.2.

The statistical analyses will only present results in Standard International (SI) standardized units. Other units will not be presented.

Only data provided by the central laboratory will be used in tables and figures. Results from local labs will be listed only.

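### The joint liver rows (possible Hy's Law, and AST/ALT with bilirubin) count only same-day central-laboratory elevations, so they can under-count; a windowed row that includes local results would close the gap

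*SAP*

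**What the plan says.** SAP 6.3.2.8 gives the purpose of the Hy's Law screen as assessing the drug's potential "to cause severe liver damage, possible Hy's Law cases will be identified". A case needs AST or ALT above 3xULN and ALP below 2xULN, "associated with an increase in total bilirubin" above 2xULN, all on one day. A second joint row, AST/ALT above 3xULN with bilirubin above 1.5x or 2xULN, has no ALP condition but the same timing rule: such elevations "on the same day will also be tabulated". The single-analyte rows (AST/ALT above 3, 5, 10 and 20xULN; bilirubin above 2xULN) have no pairing condition.

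SAP 6.3.2.1 sets the data source: "Only data provided by the central laboratory will be used in tables and figures", and "Results from local labs will be listed only". SAP 6.3.2.9 then builds both the hepatotoxicity frequency table and the flags in the laboratory listing from these definitions.

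On the protocol side, section 8.5.2 says that for safety issues, if the investigator so decides, "the local laboratory at site could be used to verify some parameters". Appendix 9 recommends close follow-up of liver signals: "Monitor 2 to 3 times per week all of the following parameters: ALT, AST, alkaline phosphatase, total bilirubin, eosinophils, INR". Section 11.1.5, which lists the liver elevations reportable as SAEs, states neither a same-day nor a laboratory-source condition.

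**The concern.** The joint rows are the part of the table that addresses severe liver injury, and a reader will look there for a zero. Two ordinary sequences can produce a zero although a subject had both elevations. In the first, the sample with both values was analysed locally. In the second, bilirubin crossed its threshold at a draw where AST/ALT had already dropped to 3xULN or below. The SAP has no pairing window, does not bring local results into these rows, and does not reconcile the rows with reported liver SAEs. The listing flags follow the same definitions, so the listing would not mark such a subject as a joint case either.

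Protocol 5.5 describes this as the first study of the compound in subjects with UC. The joint rows should not read zero merely because of a pairing rule or a data-source rule.

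**Working it through.** This is a question of case definition, so the plan has no figure to reproduce. The check applies the SAP definitions to constructed subjects.

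**Inputs.** Thresholds and the same-day rule are from SAP 6.3.2.8, the central-only rule from SAP 6.3.2.1, and the arm sizes (20 active, 10 placebo) from SAP 2.6. The laboratory values below are assumptions in multiples of ULN, with ALP at 1xULN. AT means AST or ALT; TB means total bilirubin.

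| Profile | Values | AT >3 row | Joint AT/TB >2 row | Hy's Law row |
|---|---|---|---|---|
| A | Central, one day: AT 4, TB 2.5 | counted | counted | counted |
| B | Central Day 29: AT 4, TB 1.2; central Day 36: AT 2.5, TB 2.5 | counted | missed | missed |
| C | Central Day 29: AT 4, TB 1.2; local Day 31: AT 4, TB 2.5; central Day 36: AT 2, TB 1.5 | counted | missed | missed |
| D | Local only, one day: AT 4, TB 2.5 | missed | missed | missed |

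**Which rule causes each miss**
- B is missed through the same-day rule alone. The gap is 36 - 29 = 7 days, so a window of at least 7 days recovers it.
- C and D are missed through the central-only rule alone. Each local sample shows both elevations on one day, so admitting local results recovers them with no window.
- A window without local results does not recover C, because central TB never exceeds 2xULN. Both changes are therefore needed.
- With local results admitted and a 14-day window (an assumed length; the documents give none), B, C and D are all flagged.

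**What the same-day rule does not miss.** The peaks need not coincide. Both values only have to exceed their thresholds on one central sample, with ALP below 2xULN for the Hy's Law row. A subject with ALT at 6xULN and bilirubin at 2.5xULN three days later is still counted if ALT remains above 3xULN on that later central draw and ALP is below 2xULN.

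**Size.** One uncounted case is 1/20 = 5% of the active arm or 1/10 = 10% of placebo. For the active arm, the exact one-sided 95% upper bound with 0 of 20 is 1 - 0.05^(1/20) = 13.9%. With 1 of 20 it solves (1-p)^20 + 20p(1-p)^19 = 0.05, which gives p = 21.6%.

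**The case against.** The strongest defence is that central, same-day data should capture most cases, and that the case stays visible elsewhere.

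- **Sample routing.** Protocol 8.9 sends routine safety samples to the central laboratory. Appendix 9 does not direct retests to a local one, and a home visit is a place of collection, not a laboratory. SAP 4.3.3 and 6.3.2.7 keep unscheduled data. A reader might infer that the excluded samples are those most likely to show the joint elevation; the documents do not support that.
- **Frequency.** Appendix 9 has the analytes measured together two to three times a week, which creates more same-day pairs. A reader might infer that non-coincident elevations are likely in any true case. The documents give no frequency, so they are only possible.
- **Benchmark.** The liver SAE rule in Protocol 11.1.5 is wider by design. It also admits AST/ALT at or above 8xULN alone, or at or above 3xULN with INR above 1.5, symptoms or eosinophilia. A reader might infer that every liver SAE belongs in the Hy's Law row, but many fall outside it for reasons unrelated to timing or laboratory. Whether section 11.1.5 covers elevations on different days is also a matter of interpretation, since it gives no timing.
- **Visibility.** SAEs are listed and serious TEAEs tabulated (SAP 6.3.1.8), local values are listed, central elevations appear in the single-analyte rows, and a committee reviews unblinded safety data (SAP 5).
- **False flags.** Protocol 6.1 allows documented Gilbert's disease with bilirubin above 1.5xULN at entry. A wide window makes chance pairing with a transient AST/ALT rise easier, and one false flag also moves the active arm by 5 points.

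All of this stands, and it limits the weight of the point. None of it makes the joint rows count profiles B, C or D. Central-only tables with a single reference source are a defensible default, so the remedy should add to the planned rows rather than replace them.

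**Conclusion.** The point holds as a possible under-count in the joint rows, not as loss of a case. It arises when the joint elevation is seen only locally, or when bilirubin passes 2xULN only after AST/ALT has fallen to 3xULN or below. Each such case removes 5% of the planned active arm from the rows meant to assess severe liver damage. How often this would happen cannot be estimated from the documents.

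A reader might go further and infer that one uncounted case changes the hepatic safety conclusion. The documents do not support that. Safety analysis is descriptive (SAP 6.3), and the same subject remains in the local listing or the central single-analyte rows, and in the SAE listing if reported. This is a cheap improvement that removes a possible false zero.

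**What to change.** Keep the same-day, central-only rows as planned. Add to SAP 6.3.2.8:

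- a supplementary row counting subjects with AST or ALT above 3xULN and bilirubin above 2xULN on the same day as the AST/ALT elevation or within a stated number of days after it. The sponsor should choose and justify the number before unblinding; 30 days is only an example, and is long against a 6-week treatment period;
- for this row and the matching listing flags only, use of local as well as central results, each against its own laboratory's ULN;
- identification, in the row and the listing, of subjects with raised baseline bilirubin, for example documented Gilbert's disease.

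The cost is a few lines of text and programming. Local values and ULNs must be in the database: Protocol 8.5.2 already provides for local reference ranges, and Protocol 8.2 already places protocol-specified unscheduled assessments, up to the subject's last visit, in the eCRF. The downside is a few more flagged cases to review and possible chance pairings where baseline bilirubin is raised.

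Separately, the protocol's bilirubin cut-offs for signs of liver damage differ: at or above 2.0xULN in one part of section 6.4 and in Appendix 9, at or above 1.5xULN in another part of section 6.4, and above 2xULN in section 11.1.5. These passages must be reconciled.

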### 6.3.2.9. Presentation of Results

No formal inferential statistics (p-values) will be derived.

Continuous laboratory tests including glucose, cholesterol, triglycerides, low-density lipoprotein (LDL), high-density lipoprotein (HDL) and fasted glucose will be summarized by means of descriptive statistics (including 90% CI of the mean change) by laboratory test, treatment group and analysis window. Actual values, changes from baseline and percent change from baseline will be tabulated separately. Continuous values for metabolic markers will be summarized in the PD analysis section ([section 6.5](#)).

Profile line plots by subject of all actual observed values using relative day (ADY) will be presented by treatment group. Graphs of the mean (+- SE) actual values over time and of the mean (+- SE) change from baseline, and percent changes from baseline will be presented for all continuous laboratory parameters, with the exception of the metabolic markers. Also, line plots for subjects will be provided by treatment group.

The analysis of abnormalities will focus on assessments reported during the treatment period. Results reported before baseline will only be listed.

Non-graded abnormalities and toxicities grades of the actual values will be presented as shift tables of the worst-case abnormality/toxicity grade versus the baseline abnormality/toxicity

---

 With the exception of the metabolic markers [fasted insulin, homeostatic model assessment of insulin resistance (HOMA-IR) and HbA1c] and other markers hsCRP and fecal calprotectin .

grade. The table will be created per laboratory test, treatment group and analysis period. The results of non-graded abnormalities and toxicities grades will be shown separately.

A frequency table of the number (percent) of subjects with treatment-emergent worst-case abnormalities/toxicity grade per laboratory test, treatment group and analysis period will be presented. The results of non-graded abnormalities and toxicities grades will be shown separately.

A frequency table of the number (percent) of subjects will be also provided for the hepatotoxicity flags defined before. These abnormalities will be also flagged in the individual data laboratory listing.

Listing will be provided for the laboratory test along with flag for abnormality results. In addition, pregnancy result will be listed separately.

### **6.3.3.      *Electrocardiogram***

#### **6.3.3.1.     *Available Data***

The following ECG parameters will be analysed: heart rate (HR), RR interval, PR interval, QRS interval, uncorrected QT interval, QTcF (derived)

#### **6.3.3.2.     *Derivation Rules***

##### **Derived Parameters**

The Fridericia's cube-root corrected QT (QTcF) will be calculated using the following formula.

$$\text{Fridericia's cube-root corrected QT (Fridericia, 1920): } QTcF \text{ (ms)} = QT \text{ (ms)} \times \sqrt[3]{\frac{1000}{RR \text{ (ms)}}}$$

If RR is missing, then it will be derived from HR using the formula  $RR(ms) = 60 \times HR(bpm)$ .

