| NOAEL | no-observed-adverse-effect level |
| OATP | organic anion transporter |
| OCT | organic cation transporter |
| PBMC | peripheral blood mononuclear cells |
| ██████████ | ██████████ |
| PGA | physician's global assessment |
| P-gp | permeability-glycoprotein |
| PK | pharmacokinetic(s) |
| q.d. | once daily |
| QMP | Quality Management Plan |

| | |
|------------------|---|
| RB | rectal bleeding |
| [REDACTED] | [REDACTED] |
| SAE | serious adverse event |
| SAP | statistical analysis plan |
| SF | stool frequency |
| SI | international system of units |
| SIK | salt-inducible kinase |
| SoC | standard-of-care |
| spp | species |
| SUSAR | suspected unexpected serious adverse reaction |
| $t_{1/2}$ | half-life |
| TB | tuberculosis |
| TEAE | treatment-emergent adverse event |
| Th | helper T cell |
| TMF | Trial Master File |
| TNF α | tumor necrosis factor alpha |
| T _{reg} | regulatory T cell |
| TV | target value |
| UC | ulcerative colitis |
| [REDACTED] | [REDACTED] |
| ULN | upper limit of normal range |
| [REDACTED] | [REDACTED] |
| V_{ss} | volume of distribution at steady state |
| WBC | white blood cell |

WOCBP women of childbearing potential

Definition of Terms

BMI body mass index

Weight (kg) / (height [m])²

[REDACTED]

OR

[REDACTED]

[REDACTED]

[REDACTED]

[REDACTED]

[REDACTED]

[REDACTED]
[REDACTED]

QTcF

QT interval corrected for heart rate using Fridericia's formula:

$$QTcF = QT/RR^{1/3} QT$$

RR = the interval from the onset of one QRS complex to the onset of the next QRS complex

QTv

QT interval corrected by heart rate using the van de Water formula

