8.5.4. Vital Signs

Vital signs (systolic and diastolic blood pressure taken at the same arm for each measurement, pulse, and oral/tympanic body temperature, the same method for measuring body temperature to be used throughout the study) will be recorded in a standardized manner (i.e. after the subject has rested in a seated position for at least 5 minutes) at visits specified in the Schedule of Activities in Section 8.11 (see also Section 8.1, “[Timing of Assessments](#)”). Clinically significant abnormal values should be recorded as AEs.

8.5.5. 12-lead Electrocardiogram

At the time points specified in the Schedule of Activities (see Section 8.11 and also Section 8.1, “[Timing of Assessments](#)”), a triplicate 12-lead ECG will be recorded and results will be sent for central reading.

12-lead ECG recordings will be performed before blood sampling and after subjects rested for at least 5 minutes in supine position. In case an indwelling catheter is used, ECGs may be recorded after blood sampling, provided that there is at least 30 minutes between catheter insertion and the ECG recording. When catheter insertion would fail, the 12-lead ECG needs to be taken before the venipuncture and at least 30 minutes after the failed attempt. Triplicate ECGs will be performed at the time points specified in the Schedule of Activities (see Section 8.11 and also Section 8.1, “[Timing of Assessments](#)”) preferably within a time span of 10 minutes, with an approximate 3-minute interval between ECGs.

The following parameters need to be recorded: heart rate, PR interval, RR interval, QRS interval, uncorrected QT interval, morphology and rhythm analysis. QTcF will be derived. QTcF will be considered as normal if ≤ 450 ms (male) and ≤ 460 ms (female), while a prolongation of QTcF to >500 ms or an increase from baseline >60 ms will be considered a threshold of concern.

The ECG will be reviewed centrally to detect clinically significant abnormalities. This review during the visit needs to be documented in the subject’s source. After receipt of the central report, also all flagged ECG abnormalities need to be assessed by the investigator on clinical relevance. Clinically significant abnormal values should be recorded as AEs.

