#### **6.3.3.3.     *Abnormalities***

The actual analysis values and changes from baseline of the QT and QTcF parameters will be categorized into the abnormality classes as defined in the SAP [Appendix II](#).

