CTX Type I Collagen (20y - 30y) male	NA	NA	NA	NA	> 677 pg/mL	NA	NA	NA
CTX Type I Collagen (30y - 51y) male	NA	NA	NA	NA	> 685 pg/mL	NA	NA	NA
CTX Type I Collagen (> 51y) female	NA	NA	NA	NA	> 1009 pg/mL	NA	NA	NA
CTX Type I Collagen (51y - 71y) male	NA	NA	NA	NA	> 705 pg/mL	NA	NA	NA

Parameter	L1	L2	L3	L4	H1	H2	H3	H4
CTX Type I Collagen (>71y) male	NA	NA	NA	NA	> 855 pg/mL	NA	NA	NA

**Table 3** Gradings for Urine Analysis Parameters

Parameter	L1	L2	L3	L4	H1	H2	H3	H4
Urine erythrocytes	NA	NA	NA	NA	≥ULN	≥10 cells/HPF	NA	NA
Urine protein	NA	NA	NA	NA	1+ proteinuria	2+ and 3+ proteinuria; urinary protein <3.5 g/24 hrs	urinary protein ≥3.5 g/24 hrs; 4+ proteinuria	NA
Urine glucose	NA	NA	NA	NA	>ULN (presence of glucose)	NA	NA	NA

LLN: lower limit of normal, ULN: upper limit of normal, NA: not applicable.

Any laboratory parameter with treatment-emergent (i.e., worsening from baseline) abnormalities of grade 2 or above (ie, H2/L2 or higher/lower) should be considered a 'marked laboratory abnormality'. Marked laboratory abnormalities should be described in a corresponding section of the CSR as per ICH E3 guidance, section 12.4.2.3.

**APPENDIX II: Vital Signs and Electrocardiogram grading****Table 4 Gradings for Vital Signs and Electrocardiogram Parameters**

Parameter	L1	L2	L3	L4	H1	H2	H3	H4
Systolic blood pressure (mmHg)	<90	<60	NA	NA	NA	≥140	≥160	≥180
Diastolic blood pressure (mmHg)	<60	<45	NA	NA	NA	≥90	≥100	≥120
Heart rate (bpm)	<60	<50	<40	NA	>100	>115	>130	NA
Body temperature (°C)	NA	<35	NA	NA	>38	NA	NA	NA
Respiratory rate (breaths per minute)	<12	NA	NA	NA	>20	NA	NA	NA
O 2 saturation (%)	<95	<90	NA	NA	NA	NA	NA	NA
Weight	≥7% decrease from baseline	NA	NA	NA	≥7% increase from baseline	NA	NA	NA
QTc interval on ECG (ms)	NA	NA	NA	NA	>450	>480	>500	NA
QTc change from baseline (ms)	NA	NA	NA	NA	NA	>30	>60	NA
PR interval on ECG (ms)	<110	NA	NA	NA	>200	NA	NA	NA

Parameter	L1	L2	L3	L4	H1	H2	H3	H4
QRS complex on ECG (ms)	<60	NA	NA	NA	>120	NA	NA	NA

Source: FRM-MED-005/006, valid on 08JUL2020.

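### The SAP's fallback for a missing RR interval multiplies 60 by heart rate instead of dividing 60000 by it, so QTcF computed this way is far too low

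*SAP*

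**What the plan says.** SAP 6.3.3.2 states that Fridericia's "cube-root corrected QT (QTcF) will be calculated using the following formula": QTcF(ms) = QT(ms) × cube root of (1000/RR(ms)). It then adds "If RR is missing, then it will be derived from HR using the formula" RR(ms) = 60 × HR(bpm). The section on triplicates that follows derives parameters for each tracing first and averages afterwards.

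The protocol's Definition of Terms fixes what RR means: "RR = the interval from the onset of one QRS complex to the onset of the next QRS complex". Protocol 8.5.5 lists what has to be captured: "heart rate, PR interval, RR interval, QRS interval, uncorrected QT interval, morphology and rhythm analysis. QTcF will be derived". It also sets the level that matters: "prolongation of QTcF to >500 ms or an increase from baseline >60 ms will be considered a threshold of concern".

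SAP 6.3.3.3 says "The actual analysis values and changes from baseline of the QT and QTcF parameters will be categorized" using Appendix II. There the QTc classes are above 450, 480 and 500 ms for values, and above 30 and 60 ms for change from baseline.

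**The concern.** RR is the time between beats, so it must shorten as rate rises. At HR beats per minute it is 60/HR seconds, or 60000/HR milliseconds. The SAP multiplies where it should divide and omits the factor of 1000 that turns seconds into milliseconds.

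The result goes straight into Fridericia's formula and from there into the mean-change summaries and the shift, worst-case and treatment-emergent tables. A post-baseline value computed this way makes a prolonged QTcF look normal or short. Because the worst case is the highest post-baseline value, an understated value also drops out of the worst-case selection whenever a correct one exists. A baseline value computed this way does the reverse and manufactures an increase.

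The SAP has no stated backstop for QTcF. Appendix II has no low QTc class, and section 4.3.8 keeps all outliers. With 20 active and 10 placebo subjects planned, one misclassified subject moves an incidence by 1/20 = 5 or 1/10 = 10 percentage points.

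**Working it through.** **Inputs.** The conversion rule and the Fridericia formula are from SAP 6.3.3.2, the definition of RR from the protocol's Definition of Terms, and the QTc classes from SAP Appendix II. The documents give no heart-rate distribution, so 40 to 100 bpm is assumed as a range.

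**Step 1: the conversion.** Correct: RR = 60000/HR. SAP: RR = 60 × HR. At 60 bpm these give 1000 ms and 3600 ms. They agree only where 60000/HR = 60 × HR, that is at HR = √1000 = 31.6 bpm.

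**Step 2: effect on QTcF.** QT cancels, so

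SAP QTcF / correct QTcF = [(60000/HR) / (60 × HR)]^(1/3) = (1000/HR²)^(1/3) = 10/HR^(2/3).

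| HR (bpm) | Correct RR (ms) | SAP RR (ms) | Ratio | QT 400: correct QTcF | QT 400: SAP QTcF | True 500 ms reported as |
|---|---|---|---|---|---|---|
| 40 | 1500 | 2400 | 0.855 | 349 | 299 | 427 |
| 50 | 1200 | 3000 | 0.737 | 376 | 277 | 368 |
| 60 | 1000 | 3600 | 0.652 | 400 | 261 | 326 |
| 75 | 800 | 4500 | 0.562 | 431 | 242 | 281 |
| 100 | 600 | 6000 | 0.464 | 474 | 220 | 232 |

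**Step 3: a prolonged case.** QT 470 ms at 75 bpm. Correct: 470 × (1000/800)^(1/3) = 506 ms, above the 500 ms class. SAP: 470 × (1000/4500)^(1/3) = 285 ms, no class at all. For a record to be classed above 450 ms under the SAP rule, the true QTcF would have to exceed 450/0.855 = 526 ms at 40 bpm, 690 ms at 60 bpm or 800 ms at 75 bpm.

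**Step 4: one tracing of three without RR.** With a true QTcF of 510 ms, the triplicate mean is 510 × (2 + ratio)/3. This gives 451 ms at 60 bpm and 436 ms at 75 bpm. The flag above 500 ms is lost in both; at 60 bpm the mean is still just above 450 ms.

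**Step 5: only the baseline affected.** Take a true QTcF of 400 ms at both times. If all baseline tracings lack RR, the false increase is 400 × (1 − ratio): 58 ms at 40 bpm, 139 ms at 60, 175 ms at 75 and 214 ms at 100. If one of three lacks RR, it is a third of that: 46 ms at 60 bpm, 58 ms at 75 and 71 ms at 100.

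**The case against.** The best defence is that this is a fallback. Protocol 8.5.5 requires both heart rate and RR from triplicate ECGs sent for central reading, so records with a heart rate but no RR may be rare or absent. This stands, and no frequency can be given from the documents.

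Other protections are real but partial:

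- Uncorrected QT is categorized as well and does not use RR.
- Central reading and investigator assessment of flagged abnormalities continue, and ECG interpretations are tabulated.
- Original triplicate members are listed and individual profiles plotted, so a QTcF of 220 to 285 ms might be noticed.
- Nothing says that on-study ECG review or the discontinuation criterion in protocol 6.4 uses the SAP fallback. The demonstrated harm is to the reported safety tables.

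The size also depends on circumstances. Averaging cuts the error to a third when one tracing of three is affected. A false baseline shift above 60 ms therefore needs either a fully affected baseline at more than about 40 bpm or, with one tracing affected, a faster rate (58 ms at 75 bpm, 71 ms at 100, for a true 400 ms). Below 31.6 bpm the SAP value is slightly too high (ratio 1.036 at 30 bpm).

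Finally, the formula was machine-read and the detailed derivation document is not available. If the printed operator were a division sign, RR would be 1000 times too small and QTcF ten times too high. The rule would still be wrong, in the opposite direction. The extracted symbol is an explicit multiplication sign, and the formula above it was read correctly.

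These points limit how often and how strongly the error acts. None makes the rule correct.

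**Conclusion.** The concern holds. The conversion in SAP 6.3.3.2 is wrong in units and direction, and nothing else in the documents corrects it. For records with RR missing and a heart rate above 31.6 bpm, QTcF is too low by a factor of 10/HR^(2/3): 26% too low at 50 bpm, 35% at 60, 44% at 75 and 54% at 100. After baseline this conceals prolongation in the QTcF tables; at baseline it creates false increases.

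The factors follow from arithmetic alone. The worked examples assume the QT values and heart rates shown, and the triplicate examples assume equal true values across tracings. The number of records affected is unknown. It must be fixed because the rule was written for exactly this situation and gives a misleading value when used; leaving QTcF missing would be safer.

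**What to change.** Replace the conversion in SAP 6.3.3.2 with RR(ms) = 60000 / HR(bpm). Check the printed SAP, the separate derivation document and the ECG program for the same line, because a program that silently uses the right conversion would contradict the approved SAP. Count the ECG records, baseline and post-baseline, where RR is missing and heart rate is present, so that the report can say how many QTcF values rest on the fallback. The cost is one line of text, one line of code and a short data check. No data collection or design change is involved.
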